5.2 Trial Treatments

The treatment to be used in this trial is outlined below in Table 2

Table 2 Trial Treatment

Drug	Dose/Potency	Dose Frequency	Route of Administration	Regimen/Treatment Period	Use
Pembrolizumab	200 mg	Q3W	IV infusion	Day 1 of each 3 week cycle	Experimental
Oxaliplatin	130 mg/m ²	Q3W	IV infusion	Day 1 of each 3 week chemo cycle	Combination agent
Capecitabine (Xeloda)	625mg/m ²	BID, day 1-21	PO administration	Day 1-21 of each 3 week chemo cycle	Combination agent
Epirubicin	50mg/m ²	Q3W	IV infusion	Day 1 of each 3 week chemo cycle	Combination agent

Trial treatment should begin on the day of randomization or as close as possible to the date on which treatment is allocated/assigned.

5.2.1 Dose Selection/Modification

5.2.1.1 Dose Selection

The rationale for selection of doses to be used in this trial is provided in Section 4.0 – Background and Rationale.

Details on preparation and administration of pembrolizumab (MK-3475) are provided in the Pharmacy Manual. Preparation and administration of the chemotherapy agents used in Cohort 2 should be completed as per the approved product label. See Sections 5.2.2.2 –5.2.2.4 for general recommendations for administration.

Body surface area (BSA) in m² should be calculated per local guidance.

5.2.1.2 Dose Modification (Escalation/Titration/Other)

The Common Terminology Criteria for Adverse Events version 4.0 (CTCAE 4.0) must be used to grade the severity of adverse events.

If appropriate, the Investigator may attribute each toxicity event to any of the individual chemotherapy agents used or pembrolizumab alone in the combination arms and use stepwise dose modifications according to Table 3. Pembrolizumab dose reductions are not permitted. Pembrolizumab treatment may be interrupted or discontinued due to toxicity.

If a dose level reduction for toxicity occurs with any agent, the dose may not be re-escalated. Dose modifications are always based on the previous cycle.

Subjects may have up to 2 dose level reductions per chemotherapy agent throughout the course of the study, as described in Table 3 with the exception of Epirubicin. If further toxicity occurs or the criteria for resuming treatment are not met, the subject must be discontinued from chemotherapy treatment. Of note, in the event a subject is discontinued from chemotherapy treatment, the subject may still be eligible for continued treatment with pembrolizumab (Dose Level -3 in Table 3). Refer to Table 4, and Table 5 for dose modification guidelines for adverse events for pembrolizumab; other chemotherapy will be modified per institutional standards and package labeling. If a subject experiences several toxicities and there are conflicting recommendations, follow the most conservative dose adjustment recommended (dose reduction appropriate to the most severe toxicity).

Reduction or with-holding of one chemotherapy agent and not the other agent is appropriate if, in the opinion of the Investigator, the toxicity is definitely related to one of the study treatments. If, in the opinion of the Investigator, the toxicity is related to the combination of two chemotherapy agents, both treatments should be reduced (if applicable), interrupted or discontinued according to recommended dose modifications. If the toxicity is related to the combination of three agents, all three agents should be reduced or held according to the recommended dose modifications.

Exceptional circumstances to following the dose modification tables below may be considered after consultation with the Sponsor Investigator.

Table 3 Dose modifications for Trial Medications

Drug	Starting Dose	Dose Level - 1	Dose Level - 2	Dose Level -3
------	---------------	----------------	----------------	---------------

Pembrolizumab	200 mg fixed dose	Dose reductions are not permitted	Dose reductions are not permitted	Dose reductions are not permitted
Oxaliplatin	130 mg/m2	110 mg/m2	90 mg/m2	Discontinue
Capecitabine (Xeloda)	625mg/m2 BID	500 mg/m2 BID	375 mg/m2 BID	Discontinue
Epirubicin	50mg/m2	40 mg/m2	discontinue	N/A

Capecitabine treatment may be shortened to 14 days at any currently treated dose level at the discretion of the treating physician based on toxicity assessment. Epirubicin may be excluded from the initial treatment regimen at the discretion of the treating physician, or the starting dose may be reduced to 40 mg/m2 (dose level -1), at the discretion of the treating physician.

If a toxicity is not otherwise specified, investigators should refer to the label or local standard of care for dose adjustments. At the Investigator's discretion, dose modification according to Table 3 is allowed for intolerable Grade 2-3 toxicities that are not specified in the tables below. These dose modification decisions must be documented in the subject's study records.

5.2.1.2.1 Dose Modification for Pembrolizumab

Adverse events (both non-serious and serious) associated with pembrolizumab exposure may represent an immunologic etiology. These adverse events may occur shortly after the first dose or several months after the last dose of treatment. Pembrolizumab must be withheld for drug-related toxicities and severe or life-threatening AEs as per Table 4 below. Pembrolizumab will be permanently discontinued for any severe or Grade 3 (grade 2 for pneumonitis) drug-related AE that recurs or any life-threatening event. See Section 5.6 for supportive care guidelines, including use of corticosteroids.

Table 4 Dose Modification Guidelines for Drug-Related Adverse Events for Pembrolizumab

Toxicity	Hold Treatment For Grade	Timing for Restarting Treatment	Treatment Discontinuation
Diarrhea/Colitis	2-3	Toxicity resolves to Grade 0-1	Toxicity does not resolve within 12 weeks of last dose or inability to reduce corticosteroid to 10 mg or less of prednisone or equivalent per day within 12 weeks
	4	Permanently discontinue	Permanently discontinue
AST, ALT, or Increased Bilirubin	2	Toxicity resolves to Grade 0-1	Toxicity does not resolve within 12 weeks of last dose
	3-4	Permanently discontinue (see exception below) ^a	Permanently discontinue
Type 1 diabetes mellitus (if new onset) or Hyperglycemia	T1DM or 3-4	Hold pembrolizumab for new onset Type 1 diabetes mellitus or Grade 3-4 hyperglycemia associated with evidence of beta cell failure	Resume pembrolizumab when patients are clinically and metabolically stable

Toxicity	Hold Treatment For Grade	Timing for Restarting Treatment	Treatment Discontinuation
Hypophysitis	2-4	Toxicity resolves to Grade 0-1. Therapy with pembrolizumab can be continued while endocrine replacement therapy is instituted	Toxicity does not resolve within 12 weeks of last dose or inability to reduce corticosteroid to 10 mg or less of prednisone or equivalent per day within 12 weeks
Hyperthyroidism	3	Toxicity resolves to Grade 0-1	Toxicity does not resolve within 12 weeks of last dose or inability to reduce corticosteroid to 10 mg or less of prednisone or equivalent per day within 12 weeks
	4	Permanently discontinue	Permanently discontinue
Hypothyroidism		Therapy with pembrolizumab can be continued while thyroid replacement therapy is instituted	Therapy with pembrolizumab can be continued while thyroid replacement therapy is instituted
Infusion Reaction	2 ^b	Toxicity resolves to Grade 0-1	Permanently discontinue if toxicity develops despite adequate premedication
	3-4	Permanently discontinue	Permanently discontinue
Pneumonitis	2	Toxicity resolves to Grade 0-1	Toxicity does not resolve within 12 weeks of last dose or inability to reduce corticosteroid to 10 mg or less of prednisone or equivalent per day within 12 weeks
	3-4	Permanently discontinue	Permanently discontinue
Renal Failure or Nephritis	2	Toxicity resolves to Grade 0-1	Toxicity does not resolve within 12 weeks of last dose or inability to reduce corticosteroid to 10 mg or less of prednisone or equivalent per day within 12 weeks
	3-4	Permanently discontinue	Permanently discontinue
All Other Drug-Related Toxicity ^c	3 or Severe	Toxicity resolves to Grade 0-1	Toxicity does not resolve within 12 weeks of last dose or inability to reduce corticosteroid to 10 mg or less of prednisone or equivalent per day within 12 weeks
	4	Permanently discontinue	Permanently discontinue

Note: Permanently discontinue for any severe or Grade 3 drug-related AE that recurs or any life-threatening event.

^a For patients with liver metastasis who begin treatment with Grade 2 AST or ALT, if AST or ALT increases by greater than or equal to 50% relative to baseline and lasts for at least 1 week then patients should be discontinued.

^b If symptoms resolve within one hour of stopping drug infusion, the infusion may be restarted at 50% of the original infusion rate (e.g., from 100 mL/hr to 50 mL/hr). Otherwise dosing will be held until symptoms resolve and the subject should be premedicated for the next scheduled dose; Refer to Table 5 Infusion Reaction Treatment Guidelines **Error! Reference source not found.** for further management details.

^c Patients with intolerable or persistent Grade 2 drug-related AE may hold study medication at physician discretion. Permanently discontinue study drug for persistent Grade 2 adverse reactions for which treatment with study drug has been held, that do not recover to Grade 0-1 within 12 weeks of the last dose.

5.2.1.2.2 Dose Modifications for Chemotherapy

Standard of care chemotherapy will be utilized in this protocol and modifications are allowed based on guidance detailed in Table 3 at the discretion of the treating investigator and per standard package instructions. Permanent discontinuation of any agent should be considered for any severe or life-threatening event.

Dosing interruptions are permitted in the case of medical / surgical events or logistical reasons not related to study therapy (e.g., elective surgery, unrelated medical events, patient vacation, and/or holidays). Subjects should be placed back on study therapy within 3 weeks of the scheduled interruption, unless otherwise discussed with the Sponsor-Investigator. The reason for interruption should be documented in the patient's study record.

5.2.2 Timing of Dose Administration

All trial treatments should be administered in the order presented below on an outpatient basis.

Cycle 1 Day 1:

Study treatment with pembrolizumab must be administered on Day 1 Cycle 1, after all procedures/assessments have been completed as detailed on the Trial Flow Chart (Section 6.0), followed by oxaliplatin and capecitabine. Chemotherapy may be administered up to 3 days after the scheduled Day 1 of each cycle due to administrative reasons.

Cycle 2 Onwards:

Study treatment with pembrolizumab, followed by oxaliplatin and capecitabine, may be administered up to 3 days before or after the scheduled Day 1 of each cycle for administrative reasons. It is not required that pembrolizumab is given on the same day as IV chemotherapy, but it must be administered before IV chemotherapy is administered in each cycle.

Dosing interruptions are permitted in the case of medical / surgical events or logistical reasons not related to study treatment (e.g., elective surgery, unrelated medical events, subject vacation, and/or holidays). Subjects may restart study treatment as soon as clinically appropriate at the Investigator discretion, and not exceeding 3 weeks from the interrupted dosing. Discussion with the Sponsor-Investigator must occur if the Investigator determines a subject cannot restart study medication within 3 weeks. The reason for interruption must be documented in the subject's study record.

Surgical Resection

Should occur 4-6 weeks following the last chemotherapy dose. Tissue will be collected for correlative studies.

Post-operative therapy

Should begin 6-10 weeks following resection. The dose of chemotherapy can be adjusted down 1 level or omitted at the treating physician's discretion. Pembrolizumab may be administered without chemotherapy in the post-operative setting.

5.2.2.1 Pembrolizumab

Pembrolizumab 200 mg will be administered as a 30 minute IV infusion every 3 weeks. Sites should make every effort to target infusion timing to be as close to 30 minutes as possible. However, given the variability of infusion pumps from site to site, a window of -5 minutes and +10 minutes is permitted (i.e., infusion time is 30 minutes: -5 min/+10 min).

The Pharmacy Manual contains specific instructions for the preparation of the pembrolizumab infusion fluid and administration of infusion solution.

5.2.2.2 Chemotherapy Administration

All sites will administer pembrolizumab in combination with epirubicin (when appropriate), oxaliplatin and capecitabine as the combination chemotherapy regimen. Administration of oxaliplatin and epirubicin (when appropriate) should begin on Day 1 of each three week cycle,

as detailed in Table 3 and the Trial Flow Chart (Section 6.0). Administration of capecitabine should begin on Day 1 of each three week cycle following administration of oxaliplatin, as detailed in Table 3 and the Trial Flow Chart (Section 6.0). Please refer to the product label for additional guidance on administration procedures for oxaliplatin, capecitabine, and epirubicin.

5.2.3 Trial Blinding/Masking

This is an open-label trial; therefore, the Sponsor-Investigator, investigator and subject will know the treatment administered.

5.3 Randomization or Treatment Allocation

Subjects participating in this trial will be allocated by non-random assignment.

5.4 Stratification

No stratification based on age, sex, or other characteristics will be used in this trial.

5.5 Concomitant Medications/Vaccinations

Medications or vaccinations specifically prohibited in the exclusion criteria are not allowed during the ongoing trial. If there is a clinical indication for one of these or other medications or vaccinations specifically prohibited during the trial, discontinuation from trial therapy or vaccination may be required. The investigator should discuss any questions regarding this with the Merck Clinical team. The final decision on any supportive therapy or vaccination rests with the investigator and/or the subject's primary physician. However, the decision to continue the subject on trial therapy or vaccination schedule requires the mutual agreement of the investigator, the Sponsor-Investigator and the subject.

5.5.1 Acceptable Concomitant Medications

All treatments that the investigator considers necessary for a subject's welfare may be administered at the discretion of the investigator in keeping with the community standards of medical care. All concomitant medication will be recorded on the case report form (CRF) including all prescription, over-the-counter (OTC), herbal supplements, and IV medications and fluids. If changes occur during the trial period, documentation of drug dosage, frequency, route, and date may also be included on the CRF.

All concomitant medications received within 28 days before the first dose of trial treatment and 30 days after the last dose of trial treatment should be recorded. Concomitant medications administered after 30 days after the last dose of trial treatment should be recorded for SAEs and ECIs as defined in Section 7.2.

5.5.2 Prohibited Concomitant Medications

Subjects are prohibited from receiving the following therapies during the Screening and Treatment Phase (including retreatment for post-complete response relapse) of this trial:

- Antineoplastic systemic chemotherapy or biological therapy
- Immunotherapy not specified in this protocol
- Chemotherapy not specified in this protocol
- Investigational agents other than pembrolizumab
- Radiation therapy
 - Note: Radiation therapy to a symptomatic solitary lesion or to the brain may be allowed at the investigator's discretion.
- Live vaccines within 30 days prior to the first dose of trial treatment and while participating in the trial. Examples of live vaccines include, but are not limited to, the following: measles, mumps, rubella, varicella/zoster, yellow fever, rabies, BCG, and typhoid vaccine.
- Systemic glucocorticoids for any purpose other than to modulate symptoms from an event of clinical interest of suspected immunologic etiology. The use of physiologic doses of corticosteroids may be approved after consultation with the Sponsor-Investigator.

Subjects who, in the assessment by the investigator, require the use of any of the aforementioned treatments for clinical management should be removed from the trial. Subjects may receive other medications that the investigator deems to be medically necessary.

The Exclusion Criteria describes other medications which are prohibited in this trial.

There are no prohibited therapies during the Post-Treatment Follow-up Phase.

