2.0 TRIAL DESIGN

2.1 Trial Design

This is a non-randomized, multi-site, open-label trial of pembrolizumab and chemotherapy in subjects with gastric or gastroesophageal junction adenocarcinoma. Up to 38 subjects may be enrolled in a single cohort, for a sample of 28 evaluable subjects, to assess the efficacy of combination therapy with standard peri-operative chemotherapy in resectable gastric or GE junction adenocarcinoma. The trial was initiated at 2 sites and two additional sites were subsequently added to increase enrollment.

All study subjects will receive standard of care chemotherapy for 3 cycles prior to and 3 cycles following surgery in combination with Pembrolizumab with an additional cycle of Pembrolizumab (4 total) in the pre-operative period. Additionally, subjects will complete 12 months of maintenance Pembrolizumab (14 additional doses to complete 17 post-operative cycles) following completion of post-operative chemotherapy. The primary efficacy endpoint will be **pathologic complete response (pCR) rate** among all enrolled subjects. Recurrence or disease progression will be determined based on RECIST 1.1 and investigator assessment.

Adverse events will be monitored throughout the trial and graded in severity according to the guidelines outlined in the NCI Common Terminology Criteria for Adverse Events (CTCAE) version 4.0.(As referenced in Appendix 13.2)

After the end of treatment, each subject will be followed for 30 days for adverse event monitoring. Serious adverse events and Events of Clinical Interest (ECI) will be collected for 90 days after the end of treatment or 30 days after the end of treatment if the subject initiates new anticancer therapy, whichever is earlier. Subjects who discontinue treatment for reasons other than disease recurrence will have post-treatment follow-up for disease status until disease recurrence, withdrawing consent, or becoming lost to follow-up. All subjects will be contacted by telephone for overall survival until death, withdrawal of consent or the end of the study, whichever comes first.

[figure not shown]

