5.8 Subject Withdrawal/Discontinuation Criteria

Subjects may withdraw consent at any time for any reason or be dropped from the trial at the discretion of the investigator should any untoward effect occur. In addition, a subject may be withdrawn by the investigator or the Sponsor-Investigator if enrollment into the trial is inappropriate, the trial plan is violated, or for administrative and/or other safety reasons. Specific details regarding discontinuation or withdrawal are provided in Section 7.1.4 – Other Procedures.

Even if a subject discontinues trial treatments, they will be encouraged to continue to participate in collection of data regarding the endpoints, including DFS and OS.

A subject must be discontinued from the trial treatments for any of the following reasons:

- The subject or legal representative (such as a parent or legal guardian) withdraws consent.
- Confirmed radiographic disease progression or recurrence
- Unacceptable adverse experiences as described in Section 5.2.1.2
- Intercurrent illness that prevents further administration of treatment
- Investigator's decision to withdraw the subject
- The subject has a confirmed positive serum pregnancy test
- Noncompliance with trial treatment or procedure requirements
- The subject is lost to follow-up
- Completed 12 months of uninterrupted treatment with pembrolizumab following surgical resection or 17 administrations of study medication, whichever is later.

Note: 12 months of study medication is calculated from the date of first dose following surgical resection.

- Administrative reasons

The End of Treatment and Follow-up visit procedures are listed in Section 6.0 (TRIAL FLOW CHART) and Section 7.1.5 (Visit Requirements). After the end of treatment, each subject will be followed for 30 days for adverse event monitoring (serious adverse events will be collected for 90 days after the end of treatment as described in Section 7.2.3.1). Subjects who discontinue for reasons other than progressive disease will have post-treatment follow-up for disease status until disease progression or recurrence, withdrawing consent or becoming lost to follow-up. After documented disease progression each subject will be followed by telephone for overall survival until death, withdrawal of consent, or the end of the study, whichever occurs first.

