7.2.5.2.1 Pre-operative Treatment Period

This will begin on Cycle 1 Day 1 and as outlined will include 4 cycles of therapy. The first 3 cycles will consist of combination chemotherapy and Pembrolizumab and the 4th cycle will consist of study treatment alone with Pembrolizumab. Based on previous studies it is anticipated that subjects will proceed to surgery between 4-6 weeks following completion of perioperative chemotherapy (completion of cycle 3). The pre-operative treatment period will complete once a subject proceeds to surgical exploration.

All subjects will remain on study if they have received a single dose of study medication, even if they did not complete the full course of pre-surgical chemotherapy or combination therapy.

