8.2.5 Measurement of Effect

8.2.5.1 Definitions

Evaluable for toxicity: All patients will be evaluable for toxicity from the time of their first treatment with Pembrolizumab.

Evaluable for primary outcome (pCR):

All subjects who receive a single dose of study medication and are eligible will be considered evaluable for the primary outcome of pCR. Patients who discontinue treatment prior to surgery due to reasons other than eligibility (e.g. disease progression, toxicity, or physician discretion) will be considered as not having achieved pCR. For secondary analysis, we will consider not evaluable those who do not have a pathology report for determination of pCR or discontinue treatment prior to surgery due to reasons other than disease progression and toxicity for the estimation of pCR rate.

Evaluable for secondary outcome (RR, DFS, or OS): All subjects who receive a single dose of study medication will be included in the assessment of ORR, DFS, or OS.

Evaluable for objective response: All patients included in the study must be assessed for response to treatment if they have measurable disease at baseline.

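### Section 5.5.2 tells sites to remove from the trial a patient who needs a prohibited therapy, in conflict with the sections that keep such patients in DFS and OS follow-up

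*Combined protocol and SAP*

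**What the plan says.** Section 5.5.2 lists therapies barred during screening and treatment: other systemic anticancer therapy, other immunotherapy, investigational agents, radiation, live vaccines and most systemic glucocorticoids. It then says that subjects who, in the investigator's assessment, "require the use of any of the aforementioned treatments for clinical management should be removed from the trial". The list has exceptions. For radiation, "Radiation therapy to a symptomatic solitary lesion or to the brain may be allowed at the investigator's discretion", and steroids are accepted for immune events or, if approved, at physiologic doses.

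Other sections treat the same patient differently:

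- Section 5.5, the parent section, says that "discontinuation from trial therapy or vaccination may be required", and leaves continuation on therapy to mutual agreement.
- Section 5.8 says of subjects who stop trial treatment that "they will be encouraged to continue to participate in collection of data regarding the endpoints, including DFS and OS". Use of a prohibited therapy is not named among its reasons for mandatory discontinuation.
- Section 2.1 says "Subjects who discontinue treatment for reasons other than disease recurrence will have post-treatment follow-up for disease status", and also "All subjects will be contacted by telephone for overall survival until death", with consent withdrawal and study end as the other stopping points.
- Section 7.2.5.2.1 says "All subjects will remain on study if they have received a single dose of study medication". That sentence is written for incomplete pre-operative therapy, so 2.1 and 5.8 are the stronger support.
- Section 8.2.5.1 says "All subjects who receive a single dose of study medication will be included in the assessment of ORR, DFS, or OS", and 8.2.4 defines the analysis population in the same way.

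**The concern.** Most of the protocol distinguishes coming off treatment from coming off study. The removal sentence in 5.5.2 does not. For one patient a site can therefore find three instructions: out of the trial, off treatment but followed, or still on treatment.

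The synopsis names DFS as a key secondary outcome, and 8.2.1 estimates it by Kaplan-Meier with a 24-month figure. Under 8.1.2 only progression, recurrence and death are DFS events; new therapy is not. A patient taken off study for non-protocol chemotherapy or radiation before progression is documented would be censored, and the need for that therapy may itself signal a poor outlook. Kaplan-Meier assumes that censored patients carry the same future risk as those still followed. If they carry more, the curve is too high. With about 38 patients, a handful of such cases is enough to be visible.

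The literal reading can arise in practice. Section 5.6.2 permits corticosteroids before chemotherapy infusions, while the glucocorticoid restriction in 5.5.2 makes no exception for them. Read strictly, routine premedication would fall under the removal sentence. Those two sections also need to be reconciled.

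**Working it through.** **Plan's own figures.** The documents give no power, sample size or expected rate for DFS or OS, so there is nothing to reproduce on this point. The one stated design figure, 80% power for pCR with 3 or more of 28 responders, reproduces (exact binomial power 81.3%, alpha 0.0506) and is not affected.

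**Step 1: the rules side by side.**

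| Section | Consequence for a dosed patient |
|---|---|
| 5.5.2 | removed from the trial |
| 5.5 | trial therapy may have to stop |
| 5.8, 2.1 | off treatment, disease status and OS still followed |
| 7.2.1.5.3 | after new anticancer therapy, moves to survival follow-up |
| 8.2.4, 8.2.5.1 | analysed for DFS and OS |

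**Step 2: who could be lost.** A patient with documented progression or recurrence already has a DFS event, so later removal can affect only OS. A patient without a documented event would be censored for DFS at removal and could be lost for OS too.

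**Step 3: size for 24-month DFS.** From the documents: 38 enrolled (section 1.1) and Kaplan-Meier at 24 months (8.2.1). Assumed, because the documents are silent: k = 2, 4 or 6 removed, evenly over months 3 to 9; exponential DFS at 60% at 24 months in the others; removed patients event-free at removal, with an exponential residual time of median 4 months.

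With full follow-up, expected 24-month DFS is [(38 − k) × 0.60 + k × q] / 38. Here q is the mean chance that a removed patient is still event-free at month 24:

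q = (1/6) × (4 / ln 2) × (2^(−15/4) − 2^(−21/4)) = 0.046

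- k = 2: (21.6 + 0.092) / 38 = 0.571
- k = 4: (20.4 + 0.184) / 38 = 0.542
- k = 6: (19.2 + 0.276) / 38 = 0.513 (0.511 by simulation)

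With censoring at removal, the simulated Kaplan-Meier means are 0.605, 0.609 and 0.612. They sit slightly above 0.60 because removed patients are event-free by assumption until they leave. The bias is 3.4, 6.7 and 10.1 points.

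**Step 4: vary the unstated assumptions.** Bias in percentage points:

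| Removed patients | k = 2 | k = 4 | k = 6 |
|---|---|---|---|
| event-free, residual median 4 months | 3.4 | 6.7 | 10.1 |
| event-free, residual median 12 months | 1.7 | 3.5 | 5.1 |
| half already have a recorded DFS event, rest as row 1 | 1.7 | 3.3 | 4.8 |
| three quarters already have an event, rest as row 1 | 0.8 | 1.6 | 2.4 |
| same risk as the other patients | about 0 | about 0 | about 0 |
| all already have an event | 0 | 0 | 0 |

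With a 24-month residual median the bias is 1.5 points or less.

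**Step 5: hand check without a survival model.** Let true 24-month DFS be 19/38 = 50%, and let k patients be censored before any event, all of whom would have failed by month 24. Kaplan-Meier then gives 1 − (19 − k)/(38 − k):

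- k = 2: 1 − 17/36 = 52.8%
- k = 4: 1 − 15/34 = 55.9%
- k = 6: 1 − 13/32 = 59.4%

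The bias is 2.8, 5.9 and 9.4 points. With 15 failures instead of 19 (true DFS 60.5%), k = 6 gives 1 − 9/32 = 71.9%, a bias of about 11 points.

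If only half of the removed would have failed, k = 6 gives 1 − (19 − 3)/32 = 50.0% and no bias. With 23 failures (true DFS 39.5%) it gives 1 − (23 − 3)/32 = 37.5%, which is 2.0 points too low. The sign therefore depends on whether removed patients really do worse.

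**The case against.** A reader might infer that the plan ends all endpoint follow-up for these patients, survival calls included. The documents do not support that. Section 5.5.2 never says that follow-up stops, and its last lines refer to a post-treatment follow-up phase with no prohibited therapies. Sections 1.0 and 2.1 provide survival calls for all subjects and do not list removal under 5.5.2 as a reason to stop them. Section 7.2.1.5.3 moves a patient who starts new anticancer therapy into survival follow-up, and Table 6 schedules survival status and post-study therapy status every 12 weeks. Loss of follow-up is thus a risk of one literal reading.

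A reader might also infer that every removed patient is failing, or that DFS and OS are overstated by a known 3 to 10 points. Neither follows. The list has exceptions. Patients needing a live vaccine, or steroids for other reasons, have no stated reason to be at higher risk. Many who need other anticancer therapy will already have a recorded DFS event. The 10-point figure is the severe end of the assumptions in step 4.

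Two further objections stand. DFS and OS are secondary estimates with no planned test, and the primary pCR analysis is largely protected: under 8.2.5.1 an eligible dosed patient who stops before surgery counts as not having pCR. Also, editing 5.5.2 alone would not secure DFS, because 7.2.1.5.3 sends patients on new therapy to survival follow-up, which is by telephone, although new therapy is not a DFS event.

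What the objection leaves untouched is the conflict itself. That the other sections imply continued follow-up is what puts this sentence out of line.

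**Conclusion.** The inconsistency is real and rests on the text alone. If a site applies 5.5.2 literally, DFS follow-up may be lost for patients who need a prohibited therapy before progression is documented, and OS follow-up may be lost for any removed patient. That censoring may be informative, with upward bias if removed patients do worse.

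The size is unknown. For 2 to 6 of 38 removed, the illustrative bias in 24-month DFS runs from about 0 (same risk as the others, or event already recorded) to about 10 points (all event-free at removal, 4-month residual median). No figure was worked out for OS; the mechanism is the same. The point merits correction in the next amendment, but it does not undermine the pCR test.

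**What to change.** 1. Reword the removal sentence in 5.5.2 so that needing a prohibited therapy does not end study participation. State that disease-status (DFS) and OS follow-up continue as in 2.1 and 5.8 until an event for the endpoint concerned, consent withdrawal, loss to follow-up or study end.
2. Align 7.2.1.5.3 so that starting new anticancer therapy without documented progression or recurrence does not end disease-status follow-up.
3. Reconcile 5.5 with 5.5.2 on whether trial treatment stops, and 5.5.2 with 5.6.2 on corticosteroids before infusion. Those decisions are the sponsor's; follow-up should not depend on them.

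The cost is a few sentences in the next amendment. Sections 2.1 and 5.8 already plan this follow-up, so the first change adds no visits. The second asks only that disease status stays tracked, as 2.1 already intends, for patients who would otherwise have survival calls alone.
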